#### **11.1.5. Gastrointestinal Adverse Events**

Gastrointestinal (GI) AEs will be assessed as follows:

- Stool Consistency Questionnaire – subject completed questionnaire ([Appendix A](#))
- GI Signs and Symptoms Checklist ([Appendix B](#))
- FOBT
- Open ended questions about AEs that are indicative of gastritis
- Clinical laboratory tests (hematocrit, hemoglobin, blood urea nitrogen (BUN), creatinine, ALT, and AST)
- Endoscopy (if indicated)

A-subject completed Stool Consistency Questionnaire ([Appendix A](#)) that asks 4 questions about GI symptoms will be utilized to assess GI AEs. The responses to the questions are based on a 4-point scale with 0 being no symptom and 3 being a severe symptom. The development of a new symptom or worsening of an existing symptom will be reported as an AE.

In addition, if a subject reports of any of the signs and symptoms of gastritis or potential GI ulcer complications or has a laboratory test result indicative of blood loss as shown in the GI Signs and Symptoms Checklist ([Appendix B](#)), the study gastroenterologist sub-investigator will do a thorough evaluation of the event and perform an endoscopy if it is considered warranted. A signs and symptoms checklist will be reviewed each day starting with Day 1, and then on Days 2, 3, and 7. Presence or absence of each sign or symptom will be recorded and if appropriate, a severity assessment or clinical significance evaluation will be performed.

Clinically significant changes in hematocrit and hemoglobin are defined as decreases of at least 10 percentage points and 2 g/dL, respectively. Clinically significant changes in other clinical laboratory tests will be defined as blood urea nitrogen  $\geq 40$  mg/dL, creatinine  $\geq 1.8$  mg/dL, ALT

and AST  $\geq 3$  times the upper limit of normal. If there is evidence of gastric erosion, ulcer, or bleeding in any subject confirmed by endoscopy or FOBT, the study will be stopped.

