##### **4.7.1. Safety Pharmacology Studies**

**4.7.2. Toxicology Studies**

**4.7.2.1. Pathology Findings**

### 4.7.3. Genotoxicity Studies

### 4.7.4. Discussion of Study Design

This first-in-humans study was designed based on the data generated from toxicology and toxicokinetic studies in rats and minipigs. The starting dose and dose escalation scheme are discussed in the next section (Section 4.8). The blood collection scheme for determination of PK parameters was based on the  $t_{max}$  and  $t_{1/2}$  to ensure that sufficient samples were collected soon after dosing to determine the  $C_{max}$  and  $t_{max}$  as accurately as possible while collecting samples to 48 hours after dosing to determine the terminal elimination rate constant ( $\lambda_z$ ). Because of the potential for gastric toxicity found at higher relative doses in nonclinical species, a fecal occult blood test (FOBT), and questionnaires to assess changes in stool consistency and other GI symptoms (Appendix A and Appendix B). An endoscopy will be performed if signs gastric inflammation or erosion are reported or found on laboratory evaluation. Full blood chemistry, hematology, amylase, lipase and coagulation tests along with medical urinalysis will be performed. Vital signs will be closely monitored after dosing, and subjects will be confined to the Phase 1 unit from the start of dosing for 48 hours (more than 5 half-lives of kindolor in rats or minipigs), and then will return for final safety assessments at  $7 \pm 2$  days after clinic discharge. Given the potential for gastric toxicity, an enteric coated tablet was developed for human use.

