### **8.13.2. Dose Continuation, Dose Escalation and Study Stopping Criteria**

Continuation of dosing within a cohort, or dose escalation to sequential cohorts will stop when either:

- a) The highest dose is reached or,
- b) Clinical/laboratory/AE findings meet any of the following stopping criteria:
  - i. Two or more subjects on active medication have clinical laboratory values meeting the criteria of moderate (Grade 2) intensity
  - ii. Two or more subjects on active medication experience moderate AEs of the same type (within the same MedDRA SOC)
  - iii. One or more subjects on active medication experiences any clinical laboratory value meeting the criteria of severe (Grade 3 or 4) intensity or an AE is determined to be severe in intensity
  - iiii. Any subject has a positive FOBT
- c) The mean kindolor systemic exposure levels exceed  $AUC(T_{last})=87,550$  ng.h/mL or  $C_{max} > 13,490$  ng/mL in a single subject in a cohort.
- d) The DSMB recommends stopping escalation after review of all the data from each cohort.

The maximum tolerated dose (MTD) will be considered the highest dose where no active medication subjects meet the study stopping criteria.

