Routine monitoring visits by the clinical monitors and the sponsor will be scheduled at appropriate intervals but more frequently at the beginning of the study. A monitoring visit soon after the first two subjects have been treated is planned. At these visits, the monitors will verify that study procedures are being conducted according to the protocol guidelines, monitor eCRFs against source documents, review AEs and SAEs, and perform drug accountability. At the end of the study, they will confirm that the site has the appropriate essential documents on file, advise on storage of study records, and inspect the return and destruction records for unused investigational products.

**Sponsor Site Visits:** All investigators will allow the sponsor full access to study records during site visits by the sponsor. Visits by the sponsor will be made at a mutually convenient time and will be scheduled in advance.

**DSMB:** The UCSD DSMB will meet prior to the start of the study, and after each cohort completes the study. As each cohort completes the study, a Fast-Track unblinded statistician will generate the appropriate tables and listings including PK data and a Fast-Track physician will

compile this safety data and prepare a safety report for presentation to the DSMB in accordance with the Operating Charter and planned analyses. *Ad hoc* meetings will be convened if SAEs occur that are considered at least possibly related to the investigational product or clinical, laboratory, or AE findings meet any of the stopping criteria (see section [8.12.2](#)).

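### An endoscopy-confirmed gastric lesion stops the study under Protocol 11.1.5 but is missing from the 8.13.2 list that carries the MTD definition, so the MTD can depend on which section is read

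*Protocol*

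**What the plan says.** Protocol 11.1.5 (Gastrointestinal Adverse Events) gives a one-subject rule: "If there is evidence of gastric erosion, ulcer, or bleeding in any subject confirmed by endoscopy or FOBT, the study will be stopped". It applies to a finding from either test.

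Protocol 8.13.2 sets out its own list of stopping criteria. Its only gastric-specific item is "Any subject has a positive FOBT". The other clinical items are Grade 2 laboratory values in at least two active subjects; "Two or more subjects on active medication experience moderate AEs of the same type (within the same MedDRA SOC"); and a single Grade 3 or 4 laboratory value, or the case where "an AE is determined to be severe in intensity". Item (c) sets plasma exposure limits, and item (d) is a DSMB recommendation to stop escalation. Endoscopy, erosion and ulcer are not named.

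The same section closes with the only MTD definition: "The maximum tolerated dose (MTD) will be considered the highest dose where no active medication subjects meet the study stopping criteria".

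Protocol section 10 convenes the DSMB ad hoc for SAEs at least possibly related to the product, or when clinical, laboratory, "or AE findings meet any of the stopping criteria (see section" 8.12.2). The contents list gives 8.12.2 to the stopping criteria; the body now numbers them 8.13.2.

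On when endoscopy is done, 4.7.4 says "An endoscopy will be performed if signs gastric inflammation or erosion are reported or found on laboratory evaluation", whereas 11.1.5 has the study gastroenterologist evaluate the event and "perform an endoscopy if it is considered warranted".

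SAP 9.6, like Protocol 12.3.2, will tabulate whether a GI AE triggered a stopping criterion. Neither says which list applies, and the SAP contains no derivation of the MTD.

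**The concern.** The primary objective (Protocol 6.1, SAP 3.1) is safety and the MTD. Protocol 4.9 names local stomach toxicity, with erosions and ulcerations in both animal species, as the most notable adverse effect. Endoscopy is the procedure that can confirm such a lesion when FOBT is negative. It counts in the section that stops the study and is absent from the section that defines the MTD.

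If the two sections are not tied together, one confirmed lesion could end the study while the MTD sentence, applied to the list it sits under, does not exclude the dose at which the lesion occurred. The ad hoc DSMB call has the same gap, because it points to the same list.

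**Working it through.** **1. The two rules side by side.** Take one active subject with an endoscopy-confirmed erosion or ulcer and a negative FOBT.

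| Rule | Met by this lesion? |
|---|---|
| 11.1.5, confirmed by endoscopy or FOBT, any subject | Yes |
| 8.13.2(b)i, Grade 2 laboratory value in at least 2 active subjects | No |
| 8.13.2(b)ii, moderate AE, same SOC, at least 2 active subjects | Only if moderate and a second active subject has a moderate AE in that SOC |
| 8.13.2(b)iii, one severe AE or Grade 3 or 4 laboratory value | Only if graded severe |
| 8.13.2(b), fourth item, positive FOBT | No |
| 8.13.2(c), exposure limits | Not a lesion criterion |
| 8.13.2(d), DSMB recommendation | A board decision, not a criterion that a subject meets |

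Protocol 11.1.7 grades gastritis and gastric ulcer on CTCAE v5.0, so a confirmed lesion is not severe by definition. The gap is therefore confined to FOBT-negative, non-severe lesions and, for a moderate one, to the case with no second moderate AE in that SOC.

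**2. Effect on the MTD.** Suppose the lesion occurs at 900 mg and nothing else meets a criterion at 100, 300 or 900 mg. If the MTD sentence refers to the 8.13.2 list alone, the MTD is 900 mg. If it also takes in 11.1.5, the MTD is 300 mg. For a lesion at 1800 mg the two readings give 1800 mg and 900 mg. The data are the same and the results differ by one dose level.

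**3. The plan's own probabilities.** With 6 active subjects per dose, P(at least 1) = 1 − (1 − p)^6. At p = 10, 15, 20 and 25% this gives 46.9, 62.3, 73.8 and 82.2%, which reproduces the stated 47, 62, 74 and 82%.

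**4. Illustration only.** The documents give neither a lesion rate nor the chance f that a lesion produces a positive FOBT. I use the plan's illustrative AE rates as p and let f run from 0 to 100%. I assume that every lesion is endoscoped and confirmed, that all are of one grade, that subjects are independent, and that no other criterion is met.

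- Moderate lesions: 11.1.5 is met and 8.13.2 is not when there is exactly one lesion and it is FOBT-negative, so P = 6p(1 − p)^5 × (1 − f). At p = 10% and f = 0 this is 6 × 0.10 × 0.90^5 = 35.4%.
- Mild lesions: the gap is at least one lesion with all of them FOBT-negative, so P = (1 − pf)^6 − (1 − p)^6. At p = 10% and f = 50% this is 0.95^6 − 0.90^6 = 20.4%.

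| Per cohort | p = 10% | 15% | 20% | 25% |
|---|---|---|---|---|
| Moderate, f = 0 | 35.4% | 39.9% | 39.3% | 35.6% |
| Moderate, f = 50% | 17.7% | 20.0% | 19.7% | 17.8% |
| Mild, f = 0 | 46.9% | 62.3% | 73.8% | 82.2% |
| Mild, f = 50% | 20.4% | 24.9% | 26.9% | 27.1% |
| Either, f = 100% | 0% | 0% | 0% | 0% |

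The spread, down to zero, shows that the frequency rests on the assumed p and f and not on anything in the plan.

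**The case against.** The strongest answer is that the MTD sentence speaks of the study stopping criteria in general and does not confine itself to 8.13.2(b). Section 11.1.5 says the study stops, so it is literally such a criterion. Protocol 12.3.2 and SAP 9.6 both link endoscopy results to stopping criteria. On that reading the gap closes. The reading is available but not stated: 8.13.2 introduces its own list, the MTD sentence ends that section, and the section 10 trigger points only there. What stands is an ambiguity. A reader might infer that a dose with a confirmed lesion will be reported as tolerated, or that the MTD will be one cohort too high. The documents do not support either, because both presume which section governs.

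A reader might also infer that the DSMB is bypassed. It is not. It reviews each cohort before escalation (4.9, section 10) and can stop escalation under 8.13.2(d). The Medical Monitor advises on stopping. A lesion judged an important medical event may be an SAE (11.1.2), and if at least possibly related it calls an ad hoc meeting. These safeguards do not repair the MTD definition, which asks whether subjects meet criteria, and (d) has no escalation left to stop after 1800 mg.

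The difference over endoscopy could be taken as a conflict of equal weight. It is smaller than that. Section 4.7.4 is rationale text; 4.9 names 11.1.5 as the gastric monitoring plan; and the synopsis and the schedule footnote also make endoscopy conditional. Blinding (8.7.2) limits any difference in ascertainment between active and placebo, though not between dose levels. It bears on whether a lesion is found, not on how a confirmed one counts.

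Finally, the CTCAE v5.0 definitions are not in the documents, so which lesions would be graded non-severe cannot be checked here. That limits any estimate of frequency but not the textual gap.

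**Conclusion.** The point holds as an inconsistency that reaches the primary-objective output. For an active subject with an endoscopy-confirmed, FOBT-negative, non-severe lesion (and, if moderate, no second active subject with a moderate AE in the same SOC), 11.1.5 is met and no subject-level criterion in 8.13.2 is. The MTD then depends on the reading chosen, by one dose level where the lower cohorts are clean. The ad hoc DSMB trigger has the same gap for the lesion itself.

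Severe or FOBT-positive lesions are already covered, and routine DSMB review remains. The frequency cannot be derived from the documents; the percentages above are conditional on assumed lesion rates and FOBT positivity and run from 0% upward. The printed 8.12.2 reference is a renumbering slip that still resolves through the contents list. It does not send the reader to a different rule.

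**What to change.** Reconcile Protocol 8.13.2 and 11.1.5 so that one list governs four things: stopping, the MTD sentence, the ad hoc DSMB trigger in section 10, and the SAP 9.6 flag for a GI AE that triggered a stopping criterion. State in that list how an endoscopy-confirmed lesion counts, and have the SAP name the list from which the MTD is determined. Which rule should prevail is a clinical decision for the sponsor and is not proposed here.

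Two secondary edits: align the endoscopy sentence in 4.7.4 with 11.1.5, and change the 8.12.2 reference in section 10 to 8.13.2.

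The cost is protocol and SAP wording. No procedure is added, since endoscopy and a study gastroenterologist are already in the plan.

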#### 11.1.6. Reporting Pregnancy

Pregnancy in a study subject within 30 days after study drug administration must be reported to the investigator within 1 working day of becoming aware of the pregnancy. Subjects who become pregnant during the screening period prior to study drug administration will not be randomized to receive treatment.

If the subject becomes pregnant during the study or up 30 days after study drug administration, then a Pregnancy Reporting Form must be completed and emailed to Fast-Track within 24 hours of becoming aware of the pregnancy. Pregnancies must be followed to conclusions and an updated Pregnancy Reporting Form should be emailed to Fast-Track within 24 hours of becoming aware of the conclusion of the pregnancy.

Pregnancy in a study subject is not considered an AE. However, the medical outcome of an spontaneous abortion, stillbirth, or congenital anomaly is considered an SAE and must be reported to the sponsor within 24 hours of the site becoming aware of the event.

#### 11.1.7. Classification of Adverse Event Intensity and Relationship to Investigational Product

The severity of AEs or SAEs will be in accordance with the FDA's "Toxicity Grading Scale for Healthy Adult and Adolescent Volunteers Enrolled in Preventive Vaccine Clinical Trials". For those not listed in the guidance, the following criteria will be used:

Mild:	An event that is usually transient, requiring no special treatment, and does not generally interfere with the subject's daily activities.
Moderate:	An event that interferes with usual activities of daily living, causing discomfort but poses no significant or permanent risk of harm to the subject. The event is usually ameliorated with additional specific therapeutic intervention.
Severe:	An event that interrupts usual activities of daily living or significantly affects clinical status. The event poses a significant risk of harm to the subject and hospitalization may be required, and typically requires intensive therapeutic intervention.

However, as gastric AEs are a potential concern, and the toxicity grading scale stated above, does not cover some of the more serious gastric AEs such as gastritis and gastric ulcer, the Common Toxicity Criteria for Adverse Events Grading Scale (version 5.0) will be used for the severity of these AEs.

The investigator must assess relationship to the investigational product based on the following criteria:

Unrelated:	The subject did not receive the investigational product, the temporal sequence of the AE/SAE onset relative to administration of the investigational product is not reasonable, or there is another obvious cause of the AE/SAE.
Unlikely:	There is evidence of exposure to the investigational product but there is another more likely cause of the AE/SAE.
Possible:	There is evidence of exposure to the investigational product, the temporal sequence of the AE/SAE onset relative to administration of the investigational product is reasonable, but the AE/SAE could have been due to another equally likely cause.
Probable:	There is evidence of exposure to the investigational product, the temporal sequence of the AE/SAE onset relative to administration of the investigational product is reasonable, and the AE/SAE is more likely explained by the investigational product than by any other cause.
Definite	There is evidence of exposure to the investigational product, the temporal sequence of the AE/SAE onset relative to administration of the investigational product is reasonable, the AE/SAE is more likely explained by the investigational product than by any other cause, and the AE/SAE shows a pattern consistent with previous knowledge of the investigational product or investigational product class.

#### 11.1.8. Outcomes and Actions Taken

All unresolved AEs will be followed for a minimum of 7 days (unless the AE is an ongoing pregnancy which must be followed to conclusion) after the subject's final study visit, unless the investigator's judgment dictates otherwise, the event has resolved or stabilized prior to the 7-day period, or the subject is lost to follow-up.

Investigators are not obligated to actively seek AEs or SAEs in former study subjects that occur following the follow-up period.

For each recorded AE or SAE, the investigator must assess outcome at the time of last observation, as follows:

Fatal:	The subject died.
Resolved without Sequelae:	The AE or SAE has ended.
Resolved with Sequelae:	The AE or SAE has ended but changes are noted from baseline.
Unresolved – Ongoing:	The AE has not ended and is ongoing at the end of the reporting period (i.e., 7 days after the final Follow-up visit) and the investigator deems that further follow up is not medically required.
Unknown – Lost to Follow-up:	Lost to follow-up after repeated unsuccessful attempts to contact the subject.

If the AE was treated (medications or other physical measures), this will also be recorded.

### **11.1.9. Reporting Serious Adverse Events**

#### **11.1.9.1. 24-hour Reporting Requirements (Initial Report)**

Any SAE, including death due to any cause, which occurs to any subject from the time of signing consent through the final follow-up visit whether or not related to the investigational product, must be reported ***within 24 hours*** of knowledge of the event by completing the AE/SAE eCRF. This will trigger an automatic notification of the SAE via an email communication to the sponsor and Fast-Track. Fast-Track will notify the Medical Monitor upon receipt of the notification and coordinate communications with the Medical Monitor.

#### **11.1.9.2. 3-Day Supporting Documentation Requirements (Follow-up Report)**

Written documentation for all SAEs must be received by the Medical Monitor within 3 days of reporting the event. Required eCRF that must be completed include the following:

- AE/SAE eCRF (revised if additional information is available)
- Concomitant Medication eCRF

[figure not shown]
In addition, paper copies of the following may be requested

- Copies of source documents pertinent to the event (laboratory reports, ECG tracings, medical chart notes, etc.). These should be identified only by subject number and not include any subject identification information prohibited by Health Insurance Portability Accountability Act (HIPAA).
- Any other relevant information necessary to support the investigator's judgment regarding the SAE's relatedness severity to the investigational product OR by request of the Medical Monitor/Alternate.

These paper documents may be submitted by facsimile, as email attachments, or by attaching them to the subject's eCRF casebook.

### **11.2. Collection and Processing of Blood for PK Determinations**

Blood samples for determination of kindolor plasma concentrations will be collected by venipuncture within 15 minutes prior to dosing and at 0.25, 0.5, 1, 1.5, 2, 4, 8, 12, 24, and 48 hours after dosing. Blood will be collected as close to nominal times as possible and the date and time that each blood sample is collected will be recorded to the minute.

All plasma samples for each cohort will be analyzed for AUC(Tlast) and Cmax before enrolling the next cohort. If AUC(Tlast) exceeds 87,550 ng.h/mL or Cmax exceeds 13,490 ng/mL, then dose escalation will stop.

Further details on sample collection, processing, storage, and shipping are provided in the Manual of Procedures. Plasma concentrations will be determined using a validated liquid chromatography/mass spectrometry method.

### 11.3. Clinical Laboratory Tests

Clinical laboratory tests (Table 8) will be performed at the UCSD Medical Center clinical laboratory. The laboratory should be directly regulated by the College of American Pathologists (CAP) or Clinical Laboratory Improvement Act (CLIA) guidelines. The laboratory will need to provide a copy of current certification. Additional laboratory samples may be taken at the discretion of the investigator if the results of any tests fall outside reference ranges or clinical symptoms necessitate additional testing to ensure safety.

**Table 7: Clinical Laboratory Tests**

Hematology	Clinical Chemistry	Coagulation	Urinalysis	Other
Hematocrit Hemoglobin RBC count WBC count Absolute counts for: Neutrophils Lymphocytes Monocytes Basophils Eosinophils Platelets	Albumin ALT AST BUN Creatinine Direct Bilirubin Total Bilirubin Alkaline phosphatase CPK LDH Sodium Potassium Chloride Calcium Bicarbonate Inorganic Phosphorus Uric Acid Total Cholesterol Total Protein Glucose Triglycerides	PT aPTT Fibrinogen INR	Specific gravity pH Ketones Protein Blood Glucose Nitrites Leukocyte esterase A microscopic evaluation will be performed if blood or leukocyte esterase are detected.	Amylase Lipase

Serum creatinine levels will be used to calculate creatinine clearance (CrCl) according to the Cockcroft-Gault (1976) formula as follows:

$$\text{Males} \quad \text{CrCl (mL/min)} = \frac{(140 - \text{age in years}) \times \text{body weight in kg}}{72 \times \text{serum creatinine mg/dL}}$$

$$\text{Females} \quad \text{CrCl (mL/min)} = \frac{0.85 \times (140 - \text{age in years}) \times \text{body weight in kg}}{72 \times \text{serum creatinine mg/dL}}$$

In circumstances where creatinine clearance is overestimated when using actual weight in overweight patients, use ideal weight as the adjustment per standard practice. If estimated creatinine clearance is not overestimated using actual weight, use actual weight in the Cockcroft formula instead of the ideal body weight. This will avoid underestimations that may occur when using ideal body weight in the normal weight population while also reducing overestimations that may result when using actual weight in overweight individuals.

Ideal body weight may be used to adjust for subjects with a BMI of over 25 kg/m^2 as needed:

Estimate Ideal body weight in (kg)

Males: IBW = 50 kg + 2.3 kg for each inch over 5 feet.

Females: IBW = 45.5 kg + 2.3 kg for each inch over 5 feet.

For any laboratory test value outside the reference range that the investigator considers clinically significant:

- The investigator will repeat the test to verify the out-of-range value
- The investigator will follow the out-of-range value to a satisfactory clinical resolution
- A laboratory test value will be reported as an AE with the severity score assigned in accordance with the FDA Guidance for "Toxicity Grading Scale for Healthy Adult and Adolescent Volunteers Enrolled in Preventive Vaccine Clinical Trials"

